7.1.6 Blood Draws for Clinical Assessments

The overall amount of blood to be drawn from a single subject must not exceed 120 mL/day and 550 mL in an 8-week period for safety laboratory testing, pregnancy testing, PK analyses, exploratory CCI [REDACTED] investigation, and antibody evaluation.

7.2 Demographic and Other Baseline Characteristics

The assessments and procedures described in this section must be performed during the Screening period.

7.2.1 Demographic Data

The following demographic data will be recoded:

- Subject identifier
- Date of birth

- Sex
- Race

7.2.2 Diagnosis of Merkel Cell Carcinoma

The tumor disease information that will be documented and verified at the Screening visit for each subject includes:

- detailed history of the tumor, including histopathological diagnosis (including documentation of CK20 or other appropriate cytokeratin expression such as pancytokeratin, AE1/AE3, or Cam5.2), grading, and staging in accordance with the International Union Against Cancer Tumor Node Metastasis Classification of Malignant Tumors at diagnosis;
- all therapy used for prior treatment of the tumor (including surgery, radiotherapy and chemotherapy, immunotherapy);
- any other conditions that were treated with chemotherapy, radiation therapy, or immunotherapy;
- current cancer signs and symptoms and side effects from current and previous anticancer treatments;
- current cancer disease status; and
- for Part B M1 status must be confirmed at entry

7.2.3 Medical History

In order to determine the subject's eligibility to the trial, a complete medical history of each subject will be collected and documented during Screening, which will include, but may not be limited to, the following:

- Past and concomitant nonmalignant diseases and treatments
- All medications taken and procedures carried out within 30 days prior to Screening

For the trial entry, all the subjects must fulfill all inclusion criteria described in Section 5.3.1, and none of the subjects should have any exclusion criterion from the list described in Section 5.3.2.

7.2.4 Vital Signs and Physical Examination

Vital signs including body temperature, respiratory rate, heart rate (after 5-minute rest), and arterial blood pressure (after 5-minute rest) will be recorded at trial entry.

A complete physical examination (including, in general, appearance, dermatological, head / neck, pulmonary, cardiovascular, gastrointestinal, genitourinary, lymphatic, musculoskeletal system, extremities, eyes [inspection and vision control], nose, throat, and neurologic status) will be performed and the results documented.

The ECOG PS will be documented during the Screening phase and at each scheduled visit (if the Screening ECOG PS was performed within 3 days prior to Day 1, it does not have to be repeated at Day 1).

Body weight and height will be recorded.

7.2.5 CT or MRI Scans and Photography for Tumor Assessment at Baseline

A CT scan or MRI (if MRI is used, CT of chest is mandatory; for trial sites in Germany, only MRI is to be used) of the chest, abdomen, and pelvis (at a minimum and other established assessments of tumor burden if CT / MRI imaging is not sufficient for the individual subject, including mapping of skin lesions) will be performed within 18 days prior to trial treatment start in order to document the baseline status of the tumor disease using RECIST 1.1 target and nontarget lesions (the Screening CT / MRI does not need to be repeated if having been done within 4 weeks prior to first treatment). Baseline tumor burden should be determined as outlined in Section 7.3. A brain CT / MRI scan is required at Screening if not performed within the previous 6 weeks.

A bone scan should be done at Screening as clinically indicated.

Any skin lesions assessed by physical examination and selected as a target or nontarget lesion at Baseline will have photographic image collection performed within 18 days prior to trial treatment start in order to document the Baseline status of the tumor disease (see [Appendix IV](#)).

7.2.6 Cardiac Assessments

A 12-lead ECG will be recorded after the subject has been in a supine position breathing quietly for 5 minutes. The ECG results will be used to evaluate the heart rate, atrial ventricular conduction, QR and QT intervals, and possible arrhythmias.

7.2.7 Clinical Laboratory Tests

Blood samples will be collected at Screening for clinical laboratory parameter evaluations. These clinical laboratory test results will serve not only as the baseline values for subsequent safety clinical laboratory evaluations during the trial, but also help to make sure that each enrolled subject fulfills all the trial entry criteria and does not meet any of the trial exclusion criteria for laboratory parameters as listed in Section 5.3. Detailed description of laboratory assessments is provided in Section 7.4.3.

7.3 Assessment of Efficacy

All radiographic images and physical findings including photographs (skin lesion mapping) and physical assessments used for the determination of disease progression must be submitted to the IERC vendor and will be reviewed by an IERC (see Section 5.1.2.2). The IERC will make the determination as to whether the criteria for tumor response or progression according to RECIST 1.1 have been met.

For each subject, tumor response assessment will be performed by CT scan or MRI (if MRI is used, CT of chest is mandatory; for trial sites in Germany, only MRI is to be used) imaging of the chest/abdomen/pelvis at a minimum plus other anatomical sites as specifically required) and other established assessments of tumor burden if CT / MRI imaging is insufficient for the individual subject. All the scans performed at baseline and other imaging performed as clinically required (other supportive imaging) need to be repeated at subsequent visits. In general, lesions detected at baseline need to be followed using the same imaging methodology and preferably the same imaging equipment at subsequent tumor evaluation visits. If lesions are no longer detectable, the same anatomical sites evaluated at baseline must be followed at every tumor assessment visit using the same imaging and photography methods as used at baseline.

An examination for clinical lesions, including mapping of skin lesions, should also be conducted at each tumor assessment. For skin lesions to be identified as target lesions, a minimum longest diameter of 10 mm is required. In the case of skin lesions, documentation by color photography using standardized procedures, including an accurate measurement scale within the image, is required. Refer to [Appendix IV](#) for standardized photography procedures with detailed requirements for lesion selection and photographic image acquisition. Clinical lesions will be considered measurable only when they are superficial and visible (for example, skin nodules, palpable lymph nodes). Skin lesions can be used as target lesions using measurements by caliper if they fulfill RECIST 1.1 for target lesions. The presence of new cutaneous lesions will be considered diagnostic of progression for RECIST 1.1, and any lesions detected by physical examination only should be documented by photography.

A brain CT / MRI scan is required at Screening if not performed within the previous 6 weeks. Brain CT / MRI scans should be performed, if clinically indicated by development of new specific symptoms (for trial sites in Germany, only MRI is to be used).

A bone scan should be done at Screening and beyond as clinically indicated.

For each subject, the Investigator will designate 1 or more of the following measures of tumor status to follow for determining response: CT or MRI images of primary and/or metastatic tumor masses, physical examination findings, and the results of other assessments. All available images collected during the trial period will be considered. The most appropriate measures to evaluate the tumor status of a subject should be used. The measure(s) to be chosen for sequential evaluation during the trial have to correspond to the measures used to document the progressive tumor status that qualifies the subject for enrollment. The tumor response assessment will be assessed and listed according to the schedule of assessments (refer to [Appendix I](#)).

Tumor responses to treatment will be assigned by the IERC based on the evaluation of the response of target, nontarget, and new lesions according to RECIST 1.1 (all measurements should be recorded in metric notation, see [Eisenhauer 2009](#)).

- To assess objective response, the tumor burden at baseline will be estimated and used for comparison with subsequent measurements. At baseline, tumor lesions will be categorized in target and nontarget lesions as described in [Eisenhauer 2009](#).

Results for these evaluations will be recorded with as much specificity as possible so that pre- and post-treatment results will provide the best opportunity for evaluating tumor response.

Any CR or PR should be confirmed, preferably at the scheduled 6-week interval, but no sooner than 5 weeks after the initial documentation of CR or PR. Confirmation of PR can be confirmed at an assessment later than the next assessment after the initial documentation of PR.

The Investigator may perform scans in addition to a scheduled trial scan for medical reasons or if the Investigator suspects PD.

CCI

CCI

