- therapeutic failure (subjects may stay on treatment beyond observation of progressive disease [PD] provided there is no significant clinical deterioration);
- unacceptable toxicity; or
- any criterion for withdrawal from the trial or the study drug is fulfilled.

Significant clinical deterioration is defined as

- new symptoms or worsening of symptoms that cannot be managed by optimal supportive care or disease localization that require immediate medical or surgical intervention (for example, lesion close to the spine), and/or
- change in Eastern Cooperative Oncology Group Performance Status (ECOG PS) to ≥ 3 that lasts more than 14 days.

Decisions regarding medical management of subjects will be made by the Investigator; however, the primary and secondary endpoint determinations will be according to tumor assessments performed by the IERC.

The date of the first observation of PD by RECIST 1.1 by the IERC will be used to determine the date of the PD as well as the duration of response in all subjects, including the subjects for which treatment was maintained beyond first determination of disease progression.

Adverse events will be assessed throughout the trial period and evaluated using the National Cancer Institute (NCI) Common Technology Criteria version 4.0 (CTCAE v 4.0).

Health-related quality of life will be assessed using a generic instrument (EuroQol EQ-5D [EQ-5D]), a cancer-specific instrument including a melanoma-specific module (Functional Assessment of Cancer Therapy – Melanoma [FACT-M]), and subject interviews (optional).

In Part A there will be 1 interim analysis for futility after 20 subjects have been enrolled and observed for at least

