2.3.2 Independent Endpoint Review Committee

The Independent Endpoint Review Committee (IERC) will be composed of a minimum of 3 members for Part A, and a minimum of 4 members for Part B. The role of the IERC will be to review radiographic image findings and physical findings (skin lesion mapping / physical assessments) for the determination of the BOR and date of disease progression for each subject. The full membership, mandate, and processes of the IERC will be detailed in the IERC charter for Part A, which is a single radiology review and two-oncologist review committee, and for Part B, which is a double radiology review with adjudication and single oncologist review.

3 Background Information

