5.1.4.2 Adverse Drug Reactions Requiring Treatment Discontinuation or Modifications

The following ADRs require permanent treatment discontinuation of avelumab:

Any Grade 4 ADRs require treatment discontinuation with avelumab except for single laboratory values out of normal range that are unlikely related to trial treatment as assessed by the Investigator, do not have any clinical correlate, and resolve within 7 days with adequate medical management.

Any Grade 3 ADRs require treatment discontinuation with avelumab except for any of the following:

- Transient (≤ 6 hours) Grade 3 flu-like symptoms or fever, which is controlled with medical management
- Transient (≤ 24 hours) Grade 3 fatigue, local reactions, headache, nausea, emesis that resolves to Grade ≤ 1

- Single laboratory values out of normal range (excluding Grade ≥ 3 liver function test increase) that are unlikely related to trial treatment according to the Investigator, do not have any clinical correlate, and resolve to Grade ≤ 1 within 7 days with adequate medical management
- Tumor flare phenomenon defined as local pain, irritation, or rash localized at sites of known or suspected tumor
- Change in Eastern Cooperative Oncology Group Performance Status (ECOG PS) to ≥ 3 that does not resolve to ≤ 2 within 14 days (infusions should not be given on the following cycle, if the ECOG PS is ≥ 3 on the day of study drug administration)
- Asymptomatic Grade ≥ 3 lipase or amylase elevation not associated with clinical manifestations of pancreatitis. Medical Monitor must be consulted for such lipase and amylase abnormalities.

Any Grade 2 ADR should be managed as follows:

- Infusion should not be given in case of ongoing Grade 2 ADR on the day of study treatment administration.
- Treatment can be resumed according to the original schedule once the ADR has resolved to Grade ≤ 1 . Up to 2 subsequent study drug may be omitted. If more than 2 doses are skipped, treatment may be resumed after consultation with the Medical Monitor.

Infusion-related reactions, hypersensitivity reactions (Grades 1 to 4), tumor lysis syndrome, and irAEs should be handled according to guidelines in Sections 6.5.4.1, 6.5.4.2, 6.5.4.3, and 6.5.4.4, respectively.

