For Part B: Previous malignant disease (other than MCC) within the last 5 years with the exception of basal or squamous cell carcinoma of the skin or carcinoma in situ (skin, bladder, cervical, colorectal, breast, or low grade prostatic intraepithelial neoplasia or Grade 1 prostate cancer)
9. Prior organ transplantation, including allogeneic stem-cell transplantation

10. For Part A, known history of testing positive for HIV or known acquired immunodeficiency syndrome (AIDS) or any positive test for hepatitis B virus (HBV) or hepatitis C virus (HCV) indicating acute or chronic infection. For Part B, known history of testing positive for HIV or known AIDS or HBV or HCV infection at screening (positive HBV surface antigen or HCV RNA if anti-HCV antibody screening test positive)
11. Active or history of any autoimmune disease (except for subjects with vitiligo) or immunodeficiencies that required treatment with systemic immunosuppressive drugs
12. Known severe hypersensitivity reactions to monoclonal antibodies (Grade ≥ 3 NCI-CTCAE v 4.0), any history of anaphylaxis, or uncontrolled asthma (that is, 3 or more features of partly controlled asthma)
13. Persisting toxicity related to prior therapy Grade > 1 NCI-CTCAE v 4.0; however, sensory neuropathy Grade ≤ 2 is acceptable
14. Pregnancy or lactation
15. Known alcohol or drug abuse
16. Clinically significant (that is, active) cardiovascular disease: cerebral vascular accident / stroke (< 6 months prior to enrollment), myocardial infarction (< 6 months prior to enrollment), unstable angina, congestive heart failure (New York Heart Association Classification Class $\geq II$), or serious cardiac arrhythmia requiring medication
17. All other significant diseases (for example, inflammatory bowel disease), which, in the opinion of the Investigator, might impair the subject's tolerance of trial treatment
18. Any psychiatric condition that would prohibit the understanding or rendering of informed consent
19. Legal incapacity or limited legal capacity
20. Nononcology vaccine therapies for prevention of infectious disease (for example, seasonal flu vaccine, human papilloma virus vaccine) within 4 weeks of study drug administration. Vaccination while on trial is also prohibited except for administration of inactivated vaccines (for example, inactivated seasonal influenza vaccine)

5.4 Criteria for Randomization/Initiation of Treatment with the Investigational Medicinal Product

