6.5.3 Other Trial Considerations

The following nondrug therapies must not be administered during the trial (and within 28 days before the start of trial treatment):

- Surgery to any tumor lesion for symptom management or tumor control is not permitted during the study treatment. For any other surgical interventions planned during the study, study treatment should be delayed to allow subject's recovery, for up to a maximum of 4 weeks (also see Section 5.5.1 for details of treatment management beyond initial assessment of PD)
- Herbal remedies with immunostimulating properties (for example, mistletoe extract) or known to potentially interfere with major organ function (for example, hypericin)

- Subjects should not abuse alcohol or other drugs during the trial

Any diagnostic biopsies collected for clinical reasons during the trial should be documented as a concomitant procedure including the outcome of available pathological reports.

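### Section 7.3 makes any new skin lesion progression, so a pathology-proven non-Merkel skin tumor can be dated as first PD and cut short a response

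*Protocol*

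**What the plan says.** Protocol section 7.3 sets the rule for skin lesions found during tumor assessment: "The presence of new cutaneous lesions will be considered diagnostic of progression for RECIST 1.1". The sentence carries no histological condition. A lesion seen only on physical examination has to be photographed; a biopsy is not required.

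Pathology may still exist. Section 6.5.3 says: "Any diagnostic biopsies collected for clinical reasons during the trial should be documented as a concomitant procedure including the outcome of available pathological reports". It does not say that these results go to the IERC. Section 2.3.2 describes the committee's material as radiology plus the findings from skin mapping and physical assessment; pathology is not named.

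Exclusion criterion 8 (section 5.3.2) bars other malignancy in the past 5 years, but for Part B "with the exception of basal or squamous cell carcinoma of the skin or carcinoma in situ". The Part A version makes the same exception for basal and squamous cell skin carcinoma.

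The first progression call is final for the endpoints. The Synopsis says: "The date of the first observation of PD by RECIST 1.1 by the IERC will be used to determine the date of the PD", and applies this also to subjects treated beyond progression. In the Part B SAP (section 16.2.3), duration of response ends at the first documented objective progression or at death. Durable response, the Part B primary endpoint, needs a duration of at least 6 months (protocol section 8.3.1).

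**The concern.** The rule equates a new skin lesion with progression of the disease under study, in a population where some subjects are known to have had other skin cancers. If a new nodule is removed and reported as basal cell carcinoma, section 7.3 as worded still makes it progression, and nothing in the protocol or the SAPs directs the IERC to use the pathology report. Because the first progression date is the one analyzed, no later assessment puts it right.

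Four kinds of endpoint could be affected: duration of response and PFS in both parts; response status at 6 and 12 months; durable response in Part B, if the call comes early enough; and confirmed best overall response in Part A, if the call comes before a response is confirmed. Section 5.1 gives Part B a confirmatory role for some approvals, so its primary endpoint should not depend on an unrelated skin tumor.

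**Working it through.** **1. Is there a limit to MCC anywhere?** Reading the protocol and both SAPs for any condition on a new skin lesion:

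| Place | Content | Limits the rule to MCC? |
|---|---|---|
| Protocol 7.3 | New skin lesion is diagnostic of progression | No |
| Protocol 2.3.2 | IERC reviews images and physical findings | Pathology not named |
| Protocol 6.5.3 | Pathology of clinical biopsies is recorded | No route to the IERC |
| Protocol 8.3.2; Part A SAP 16.2.1 and 16.2.2; Part B SAP 16.2.4 | Determination of the first progression date is left to the IERC charter | No mention of lesion type |

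**2. Reproduce the plan's own figures.** Inputs from protocol section 8.1: n = 112, true durable response rate (DRR) 0.45, two-sided 95% Clopper-Pearson interval. The lower limit for x responders is the 2.5% quantile of Beta(x, 112 − x + 1).

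- Smallest x with lower limit above 20%: 32 (limit 20.4%). P(X ≥ 32 | 112, 0.45) = 0.9999. The plan states more than 99%.
- Smallest x with lower limit above 30%: 44 (limit 30.2%; 43 gives 29.4%). P(X ≥ 44 | 112, 0.45) = 0.9055. The plan states 90%.

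Both figures reproduce.

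**3. Illustrate the effect.** Let s be the share of true durable responders counted as failures because a non-MCC skin lesion was called progression less than 6 months after first response. The documents give no value for s; 2%, 5% and 10% are assumptions. The observed rate becomes p = 0.45 × (1 − s), and the expected loss is 112 × 0.45 × s subjects.

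| s | p | Expected subjects lost | P(lower limit > 30%) | P(lower limit > 20%) |
|---|---|---|---|---|
| 0 | 0.450 | 0 | 90.6% | 99.99% |
| 2% | 0.441 | 1.0 | 86.9% | 99.97% |
| 5% | 0.4275 | 2.5 | 79.8% | 99.9% |
| 10% | 0.405 | 5.0 | 63.8% | 99.7% |

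**4. The same in counts.** One subject is 1/112 = 0.9 percentage points of DRR. Starting from the plan's example of 45 durable responders, one loss leaves 44 and a lower limit still above 30% (30.2%); two losses leave 43 and a limit of 29.4%. Starting from the example of 50, it takes seven losses (50 − 43) to fall below 30%.

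**The case against.** The strongest reply is that the sentence should be read in its setting. It speaks of progression for RECIST 1.1, in a section on tumor assessment, and the same section leaves the call to the committee: "The IERC will make the determination as to whether the criteria for tumor response or progression according to RECIST 1.1 have been met". It also says: "Tumor responses to treatment will be assigned by the IERC based on the evaluation of the response of target, nontarget, and new lesions". Oncologist review is part of the process in both parts, and Part B adds two radiology readers with adjudication. The committee's processes are in a charter that is not among the documents and may already deal with attribution. This stands in part: it means that a wrong call is possible, not certain. It does not remove the gap, because a general grant of authority sits beside a specific sentence that calls the lesion diagnostic, and a charter should not have to contradict the protocol.

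A reader might infer that every new basal or squamous cell carcinoma makes a durable responder a failure. The documents do not support that. The IERC must call progression, and the call must come less than 6 months after first response. A later call shortens duration of response but leaves the subject a durable responder.

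A reader might also infer that drug rash or tumor flare would be counted as progression. Section 5.1.4.2 does mention "Tumor flare phenomenon defined as local pain, irritation, or rash localized at sites of known or suspected tumor", but that is an adverse-reaction rule about places where tumor is already known or suspected. Nothing in the documents treats rash as a RECIST lesion.

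Finally, the error can only lower DRR, so it cannot create a false positive against the 17.7% historical reference, and Part B estimates a rate without a formal test. Both points are correct, and they limit how serious the matter is.

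**Conclusion.** The gap in wording is real. As written, section 7.3 lets a skin tumor that pathology has shown not to be MCC be dated as first progression, with loss of duration of response and PFS and, within 6 months of first response, of a Part B durable response.

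The direction is conservative, and the size cannot be determined from the documents. The fall from about 90% to 87%, 80% or 64% rests wholly on the assumed shares of 2%, 5% and 10%. The admission of subjects with earlier skin carcinoma makes new ones foreseeable but gives no on-study rate. Over the same range the chance of a lower bound above 20% stays above 99%, so the comparison with the observed historical rate is hardly touched; only the 30% benchmark is sensitive. The conclusion also assumes that the charter does not already exclude proven non-MCC lesions. The issue is the accuracy and interpretation of the endpoints, not inflated efficacy. It is worth correcting because correction costs so little.

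**What to change.** Replace the sentence in section 7.3 with: *A new cutaneous lesion is progression unless available pathology shows a diagnosis other than MCC, in which case it is not a new lesion for RECIST 1.1.* Align the IERC charter if it does not already say this, and send the committee the pathology already recorded under section 6.5.3.

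A lesion without contrary pathology remains progression by default, dated to its first appearance. That default matters: in an open-label single-arm trial, allowing lesions to be discounted from photographs alone could bias the results upward.

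The cost is a small data transfer to the IERC; no added biopsies, visits or readers are needed. The limitation is that non-MCC lesions that are never biopsied still count as progression. Section 10.6.2 already cites publications for Part A, so if the new wording is applied only to Part B, the report should say that the two parts used different rules.
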